6.2.3 Exploratory Efficacy Endpoints and Analyses

Exploratory efficacy endpoints will be summarized for patients included in the mITT population. No analyses will be performed. All data will be provided in data listings.

The presence and frequency of depressive symptoms are assessed through the Patient Health Questionnaire-9 item version (PHQ9). There are 9 questions with scores ranges from 0=“not at

all” to 3=”nearly every day”. The total score is 27. Summary statistics will be presented by treatment arm for the Day 40 results.

Two Long COVID questionnaires are to be completed on Day 40, or by ePRO/telephone between Day 40 and 50. One by the patient and the other by an informant.

The Long COVID Questionnaire (LCQ) is self-administered to assess symptoms of Long COVID. The LCQ contains a series of questions asking the patient to compare current health and abilities to pre-COVID health and abilities with subscales that collect information on 1) Functioning and Performance, 2) Somatic symptoms, and 3) Cognitive complaints. The questionnaire further collects changes in life circumstances extrinsic to COVID-19 disease. The total score and scores for each subscale will be summarized descriptively by treatment arm.

Patients with clinically meaningful changes in pre-COVID health and abilities (changes in subscale 1, 2, or 3) on Day 40 will be considered as having Long COVID symptoms and will be summarized (N and %) by treatment arm.

A second Long COVID questionnaire will be completed by an informant (Long COVID Informant Questionnaire (LCIQ)). Seventeen items will be completed by the informant to understand the informant’s perspective on changes in life functioning temporally associated with COVID-19 disease onset. Responses to the items (total score and subscale scores) will be descriptively summarized by treatment arm.

6.2.4 Interim Analysis

An interim analysis will be performed once approximately 70 patients (20% of information) in the mITT population have completed the Study Day 28 assessment or who have an intercurrent event within 28 days on study leading to missing primary efficacy data. All patients up to the data cutoff date for the interim analysis will be included in the analysis. Imputation of missing data will be performed as described in Section 6.2.1.3.

Efficacy data, including the primary endpoint, and cumulative safety data will be reviewed at the time of the interim analysis by the DMC.

A non-binding one-way futility analysis will be performed. The futility boundaries were derived using custom Z-scores. The Z-score chosen as the boundary is considered clinically relevant and has a high probability of success at the final analysis with conditional power of at least 81.5%. At the time of the interim analysis, there must be at least a 7.5% treatment difference observed. Assuming the placebo event rate of 20% and INB03 event rate of 12.5%, the futility boundary will be set at $Z < -0.8505$ (one-sided test). Should the result of the primary endpoint analysis Z-statistic be greater than -0.8805 (one-sided p-value ≥ 0.1975), the futility boundary will be considered crossed, and futility assumed. At the time of interim analysis, the boundary may be recalculated based on true number of participants with evaluable data included in the interim analysis population.

In order to maintain the study blind, an independent unblinded statistical team not involved in the conduct of the study will perform the analyses and present the results to the DMC during a closed

meeting where only the DMC members and the unblinded statistician attend. Details included in the DMC charter.

The futility analysis is non-binding and the DMC will make a recommendation based on review of primary efficacy and safety data. The DMC will recommend the trial continue as planned or be terminated due to futility or safety concerns. There will be no early termination due to positive efficacy signals. The decision to terminate the trial will be at the sole discretion of the sponsor.

On 15Jun2021, the sponsor terminated enrollment into the study. Participants who were enrolled and randomized on or before 15 June were followed to study completion and will be included in the primary efficacy analysis. A total of 79 subjects were randomized, 77 receiving randomized study drug.

A preliminary analysis of the primary efficacy data will be performed prior to the final database lock. The primary efficacy endpoint will be analysed and a limited number of individuals who are not involved in the study conduct or review of day-to-day activities of the study will be informed on the unblinded efficacy results in order to plan further development and inform on other corporate objectives. The DMC will also review unblinded safety and the primary efficacy data and recommend to the sponsor their unbiased opinion concerning safety and efficacy of INB03 in an acute COVID population.

The unblinded team will provide the DMC and select individuals from INmune Bio. the unblinded primary efficacy results. Only the DMC will receive unblinded safety data. The DMC and unblinded sponsor team will collaborate directly with the unblinded statistical team for further support as needed. The statistical study team will not be in contact with the unblinded sponsor team.

A final analysis will occur once all subjects complete the study.

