9.7 Analysis and Reporting

9.7.1 Interim Analyses

An interim analysis will be performed when approximately 70 participants in the mITT population have completed the Study Day 28 assessment or who have an intercurrent event within 28 days on study (withdrawal or lost to follow-up). Imputation of missing data will be performed as described in [Section 9.5.1](#).

Efficacy data, including the primary endpoint and cumulative safety data will be reviewed at the time of the interim analysis by the DMC.

A non-binding one-way futility analysis will be performed. The futility boundaries were derived using custom Z-statistic. The Z-statistic chosen as the boundary is considered clinically relevant and has a high probability of success at the final analysis with conditional power of at least 81.5%. At the time of the interim analysis, the Z-statistic boundary was chosen based on a 7.5% treatment difference corresponding to a placebo event rate of 20% and INB03 event rate of 12.5%. The futility boundary will be set at $Z < -0.8505$ (one-sided test). Should the result of the primary endpoint analysis Z-statistic be greater than -0.8505 (one-sided p-value ≥ 0.1975), the futility boundary will be considered crossed, and futility assumed. At the time of interim analysis, the boundary may be recalculated based on true number of participants with evaluable data included in the interim analysis population.

In order to maintain the study blind, an independent unblinded statistical team not involved in the conduct of the study will perform the analyses and present the results to the DMC during a closed meeting where only the DMC members and the unblinded statistician attend.

A preliminary analysis of the primary efficacy data will be performed prior to the final database lock. The primary efficacy endpoint will be analyzed and a limited number of individuals who are not involved in the study conduct or review of day-to-day activities of the study will be informed on the unblinded efficacy results in order to plan further development and inform on other corporate objectives. The DMC will also review unblinded safety and the primary efficacy data and recommend to the sponsor their unbiased opinion concerning safety and efficacy of INB03 in an acute COVID population.

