3.3 Sample Size

A total sample size of 366 participants randomized 1:1 to treatment with either INB03 + SofC or Placebo + SofC (N=183 in each arm) will provide adequate power to compare the proportion of participants with disease progression in each group by Day 28. It is assumed that 21% of enrolled participants randomized to Placebo + SofC will progress whereas the expected disease progression rate will be reduced by two-thirds to 7% in participants randomized to INB03 + SofC. To observe the expected treatment effect, N=346 (N=173 per arm) are required.

Additionally, an interim analysis for futility will be performed once approximately 20% of participants required to observe the expected treatment effect complete the Study Day 28 visit (approximately N=70). Participants evaluated in the interim analysis include those who are randomized and receive study drug and have the Day 28 assessment or who had an intercurrent event prior to Day 28. A customized futility boundary was chosen to ensure a clinically meaningful difference between treatment arms is observed at the interim and which will provide a high conditional power at the time of the final analysis.

The proposed study with the above assumptions will have at least 90% power assuming a one-sided Z-Test with overall alpha for the study of 0.005.

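### SAP 6.2.4 gives two futility cut-offs (-0.8505 and -0.8805), words the 7.5-point derivation as a requirement, and does not say that its 81.5% conditional power assumes 21% vs 7%

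*SAP*

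**What the plan says.** SAP 6.2.4 plans a non-binding futility look at about 70 mITT participants. Assuming 20% progression on placebo and 12.5% on INB03, it sets the boundary at Z < -0.8505. The sentence that declares futility uses another number: "Should the result of the primary endpoint analysis Z-statistic be greater than -0.8805 (one-sided p-value ≥ 0.1975". The matching sentence in Protocol 9.7.1 reads "Should the result of the primary endpoint analysis Z-statistic be greater than -0.8505 (one-sided p-value ≥ 0.1975", and the protocol gives -0.8505 both times.

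Just before the boundary, the SAP says "there must be at least a 7.5% treatment difference observed". The protocol says only that the boundary was chosen from a 7.5% difference at those two rates.

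The SAP says that the chosen boundary "has a high probability of success at the final analysis with conditional power of at least 81.5" percent, and the protocol makes the same claim. Neither names the effect assumed for participants not yet observed. Both allow the boundary to be recalculated on the actual number evaluable, without giving a formula.

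**The concern.** A futility rule needs one threshold. As printed, a Z between -0.8805 and -0.8505 satisfies the boundary in one SAP sentence and is declared futile in the next. Read literally, the 7.5-point sentence adds a condition that can disagree with either Z value. The conditional power is given without the assumption behind it. A DMC member or sponsor reader could take 81.5% as the chance of success for a trial that has just shown a 7.5-point difference, when the figure needs a 14-point difference in everyone still to come. At stake is the clarity of the recommendation to the sponsor. Type I error is not affected, since the trial cannot stop early for efficacy.

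**Working it through.** **Inputs.** From SAP 3.3: "It is assumed that 21% of enrolled participants randomized to Placebo + SofC will progress", "reduced by two-thirds to 7% in participants randomized to INB03 + SofC", "N=346 (N=173 per arm) are required", and "at least 90% power assuming a one-sided Z-Test with overall alpha for the study of 0.005". From SAP 6.2.4: interim N about 70 (35 per arm), boundary rates 20% and 12.5%. The information fraction is t = 70/346 = 0.2023 and the final critical value is z = 2.576.

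**1. The boundary.** The mean of 20% and 12.5% is 0.1625. The pooled Z is -0.075 / sqrt(2 × 0.1625 × 0.8375 / 35) = -0.8505. Then Φ(-0.8505) = 0.1975, which is the printed p-value. Φ(-0.8805) = 0.1893, which is not.

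**2. Results that the two cut-offs treat differently.** Placebo vs INB03 events, unstratified pooled Z:
- 9/35 vs 6/35: Z = -0.874.
- 4/35 vs 2/35: Z = -0.854.

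Both continue under -0.8505 and are futile under -0.8805. Exact enumeration of all tables at 35 per arm under 21% vs 7% gives P(stop) = 17.3% at -0.8505 and 19.4% at -0.8805, a gap of 2.1 points.

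**3. The 7.5-point sentence against the Z rule.**
- 10/35 vs 7/35: the difference is 8.6 points, so it meets 7.5, but Z = -0.836 fails both cut-offs.
- 3/35 vs 1/35: the difference is 5.7 points, so it misses 7.5, but Z = -1.03 passes both cut-offs.

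The difference equivalent to Z = -0.8505 at 35 per arm is 5.3 points at a 10% placebo rate, 7.5 at 20% and 8.9 at 30%.

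**4. Conditional power at the boundary.** Taking benefit as positive, CP = 1 - Φ((2.576 - Z√t - θ(1 - t)) / √(1 - t)), with Z√t = 0.8505 × 0.4498 = 0.3825 and √(1 - t) = 0.8931.
- Remaining participants follow 21% vs 7%: θ = 0.14 / sqrt(2 × 0.14 × 0.86 / 173) = 3.753, and θ(1 - t) = 2.993. The argument is (2.576 - 0.3825 - 2.993) / 0.8931 = -0.896, so CP = 81.5%. This is the plan's figure.
- Remaining participants follow the boundary trend: θ = 0.8505 / 0.4498 = 1.891, and θ(1 - t) = 1.508. The argument is (2.576 - 0.3825 - 1.508) / 0.8931 = 0.767, so CP = 22.2%.

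Other variance choices and t = 0.20 move the design-effect figure only between 81.5% and 84.0%, and t = 0.20 gives 22.6% for the trend.

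**5. Recalculation at another n.** The formula in step 1 at 38.5 per arm (77 dosed) gives -0.892.

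**The case against.** The slip can be resolved from the text around it: the printed p-value, the preceding sentence and the protocol all point to -0.8505. It rarely matters, as the 2-point gap shows. The tables use an unstratified pooled Z, whereas the planned statistic is the stratified CMH, so they are illustrations only. All of this stands, and it limits the size of the point.

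On the 7.5 points, the sentence leads into the derivation, and the sentence that declares futility names only Z. That reading is reasonable and matches the protocol. The SAP's wording still states a requirement, so it needs clarifying.

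On conditional power, a reader might infer that 81.5% is an arithmetic error, overstated nearly fourfold against 22%. The documents do not support that. Conditional power under the design effect is a standard convention, the figure reproduces on it, and neither document claims it under the current trend. The trend figure extrapolates from about 20% of the information and is no more the true probability of success. A reader might also take 22% as describing this trial's data. It does not: the documents report no interim result.

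Finally, the rule is non-binding, the decision to terminate rests with the sponsor, and the SAP records that enrollment ended on 15Jun2021 with 79 randomized and 77 dosed. It adds that some of its sections may no longer apply. This reduces the severity but leaves the contradiction in current text.

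**Conclusion.** SAP 6.2.4 is wrong as written on the decision threshold: -0.8805 conflicts with its own p-value, its own derivation and Protocol 9.7.1, all of which give -0.8505. The practical effect is about 2 percentage points in the stopping probability under 21% vs 7%, assuming 35 per arm and the unstratified pooled Z. The 7.5-point sentence is not equivalent to the Z rule and should not stand as a criterion. The 81.5% is correct under 21% vs 7% with pooled variance and t = 70/346, but that assumption is unstated in both documents; under the boundary trend the figure is about 22%.

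Severity is moderate. A reader might infer that this go/no-go rule must be repaired before the trial can be interpreted. The documents do not support that: the rule is non-binding, there is no efficacy stop, and enrollment has closed.

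**What to change.** - In SAP 6.2.4, replace -0.8805 with -0.8505.
- In SAP 6.2.4, state that Z alone decides and that 7.5 points at 20% vs 12.5% is only how the boundary was derived.
- In SAP 6.2.4 and Protocol 9.7.1, label the 81.5% as conditional on the remaining participants following 21% vs 7%, and give the boundary-trend figure of about 22% beside it.
- If the boundary is recalculated for the actual number evaluable, specify the same pooled formula (-0.892 at 38.5 per arm).

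The cost is wording in the SAP and protocol, and in the DMC charter if it repeats the rule. No new data or analyses are needed. The stated prospect of success will look less favourable once its assumption is shown.

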6.2.5 Multiplicity

Formal statistical analysis will be performed for the primary efficacy endpoint. All p-values displayed for the secondary efficacy endpoints will be nominal in nature. No multiplicity adjustments will be performed for multiple analyses or multiple endpoints.

6.2.6 Subgroup Analyses

Subgroup analyses may be performed outside the scope of the SAP.

6.3 Safety

Safety assessments will include current standard of care in the hospital setting. Assessments such as vital signs will be assessed daily while the patient is in the hospital. COVID-19 labs will also be assessed every other day and additionally as requested by the physician. Safety assessments including but not limited to chest imaging, ECG, safety labs (hematology, chemistry) will be performed at the discretion of the physician.

All safety analysis reporting will be based on the Safety Population.

6.3.1 Adverse Events

Adverse events (AEs) will be recorded from study enrolment until study Day 70. AEs will be assessed for severity according to the Common Terminology Criteria for Adverse Events (CTCAE) v5.0, relationship to study drug, and seriousness. Adverse events will be considered treatment-emergent if the event was a pre-existing condition that increases in severity, becomes serious after start of study treatment, or if the onset of the event occurs after the first dose of study treatment. Any missing severity assessments will be assumed as Grade 3 severity and missing relationship assessments will be assumed as related.

An overview of treatment-emergent AEs (TEAEs) will be provided, including counts and percentages of patients with any incidences of: TEAEs, TEAEs related to study treatment, serious adverse events (SAEs), TEAEs leading to study discontinuation, SAEs, and fatal SAEs.

Adverse events will also be displayed by MedDRA coded system organ class (SOC) and preferred term (PT) in descending order of overall incidence. Data will be reported by treatment arm and overall.

Summaries of adverse events by SOC and PT will be provided for the following:

- TEAEs;
- TEAEs related to study treatment;
- CTCAE Grade 3 or higher TEAEs;
- CTCAE Grade 3 or higher TEAEs related to study treatment;
- SAEs; and
- TEAEs leading to study discontinuation.

When calculating the incidence of AEs, each AE will be counted only once for a given patient within a MedDRA category (e.g. overall, system organ class or preferred term). When AEs are summarized within levels of another AE assessment (e.g., relatedness or severity), AEs will be counted once per patient at the worst level of the assessment (e.g., strongest relationship to study drug or greatest severity).

A comprehensive listing of all AEs reported will be provided in a by-patient data listing. In addition, the following listings will be provided:

- TEAEs related to study treatment;
- SAEs;
- TEAEs leading to study discontinuation; and
- Fatal AEs.

6.3.2 Clinical Laboratory Evaluations

Safety laboratory data will be collected at the site and reported locally. Haematology and clinical chemistry are optional in reporting during the hospital setting and will be collected as per standard of care for the patient while in the index hospital. Safety laboratory collection is required at screening, upon discharge and on Day 28 and Day 40.

As collection date may vary, by-patient listings will be provided and abnormal results will be flagged. Change from baseline will be provided in the listing. A separate listing for abnormal and clinically significant lab results will be provided if there is data to support this listing.

Clinical chemistry and haematology parameters will be reported based on the International System of Units (SI).

Pregnancy test is only performed at screening in women of childbearing potential, test results will be listed.

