4 STUDY DESIGN AND ENDPOINTS

4.1 Description of the Study Design

The trial is a Phase 2, double-blind, placebo-controlled, randomized clinical trial of INB03 in participants with pulmonary complications from COVID-19 infection. Each participant will complete up to 6 study visits.

Screening: Participants with a diagnosis of COVID-19 will be screened for study eligibility. Prior to any trial related procedures, participants will provide their consent to participate in the clinical trial. Screening assessments will include:

- collection of medical history/participant demographic (including race and ethnicity);
- physical examination (including vital signs, height and weight);
- room air oxygen saturation (SaO₂), if possible;
- chest imaging;
- ECG;
- WHO Ordinal Scale for Clinical Improvement (to be completed any time after informed consent is obtained and up to 1-hour post-randomization on Day 1);
- clinical laboratory evaluations (as per [Table 2: Clinical Laboratory Evaluations](#));

CONFIDENTIAL

- serum or urine pregnancy test for women of childbearing potential (WCBP).

If any of the above assessments are performed as part of routine clinical care within 1 day of Screening, they do not need to be repeated.

Study Day 1: Eligible participants will be randomized to receive either INB03 at 1mg/kg by subcutaneous injection (SC) + standard of care (SOC) or Placebo SC injection + SOC within 1 day of Screening. Participants will receive their first dose of study drug after randomization. Blood samples to check TNF levels and perform an anti-drug antibody test will be collected before dosing. Clinical assessments while participants are inpatients will be as per routine management of hospitalized COVID-19 patients including daily collection of vital signs, physical exam, concomitant medications and laboratory evaluations. 12-lead ECGs and chest imaging assessments will be performed if deemed clinically necessary. Additionally, use of non-mechanical ventilation will be collected daily until the participant is discharged from hospital.

The WHO Ordinal Scale will also be completed daily until the participant is discharged from hospital.

The sponsor recognizes that SOC may change over time. The study protocol allows therapies that have shown benefit in well-designed prospective randomized trials. Each clinical site can select their SOC.

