4.2.3 Safety Endpoints

The safety endpoints of the study are:

- Incidence of adverse events and serious adverse events not due to underlying disease;
- Incidence of abnormal findings in clinical safety laboratory parameters, vital signs, and ECGs.

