7.1.7 Clinical Laboratory Safety Tests

Blood samples (up to 25 mL) will be collected for clinical laboratory safety tests at the timepoints specified in [Table 3](#) - SOA. A list of laboratory evaluations is provided in [Table 2: Clinical Laboratory Evaluations](#) below.

Table 2: Clinical Laboratory Evaluations

Haematology	Hematocrit	White blood cell (WBC) count
	Hemoglobin	WBC differential (absolute):
	Mean corpuscular hemoglobin	Basophils
	Mean corpuscular hemoglobin concentration	Eosinophils
	Mean corpuscular volume	Lymphocytes
	Platelet count	Monocytes
	Red blood cell (RBC) count	Neutrophils
	RBC distribution width	
Clinical Chemistry	Alanine aminotransferase (ALT)	Creatinine phosphokinase
	Albumin	Glucose
	Alkaline phosphatase	Phosphorus
	Aspartate aminotransferase (AST)	Potassium
	Calcium	Sodium
	Carbon Dioxide (CO ₂)	Total bilirubin
	Chloride	Total protein
	Creatinine	
COVID-19 Specific		At a minimum will be collected:
	eGFR	• Screening Visit
	Troponin	• Every 2 days during hospitalization
	CRP	• Discharge Visit
	Ferritin	• Day 28 Visit
	D-dimer	• Day 40 Visit
Other	Pregnancy Test (urine or serum)	To be performed for WCBP at Screening Visit
	Tumour Necrosis Factor (TNF)	To be collected: • Day 1 (before dosing with study drug)
	Anti-drug Antibody (ADA)	To be collected: • Day 1 (before dosing with study drug) • Day 28 Visit • Day 40 Visit

If laboratory evaluations are performed more than once a day as part of the routine management of hospitalized COVID-19 patients, the results from the first set of daily labs collected will be reviewed for this study and entered in the CRF.

Safety clinical laboratory samples will be analysed by the investigational site's local pathology laboratory.

The ADA test will be collected by the site and sent to the central laboratory for analysis. Instructions on collection, processing and preparation for shipment of central laboratory samples will be provided in the Central Laboratory Manual.

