9.5.4.2 Vital Signs, Electrocardiogram and Laboratory Assessments

Vital signs and laboratory tests will be summarized as absolute values and change from baseline by treatment arm. Participants with fever ($\geq 38^{\circ}\text{C}$) and days with fever will be tabulated. Baseline is defined as the latest value in the database prior to randomization. Listings of abnormal laboratory parameter results will be provided.

Electrocardiogram data collected throughout the study period will be provided in data listings.

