6.3.4 Electrocardiogram

Electrocardiogram (ECG) may be performed throughout the time the patient is in the index hospital as part of routine care. ECGs will be performed at screening, on Day 28 and Day 40. If these visits are conducted remotely, the ECG may be omitted.

Data collected in the eCRF includes the overall evaluation of the ECG, either normal, abnormal and not clinically significant or abnormal and clinically significant. Listings of data collected will be provided by patient.

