6.3.6.4 Anti-drug Antibody

The development of anti-drug antibodies will be assessed. Blood samples will be collected prior to dosing with study treatment and at the Day 28 and Day 40 visits and will be analyzed at a central laboratory. A listing of anti-drug antibody data will be provided.

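### No SAP output gives, by arm, how many participants had an abnormal laboratory, vital-sign or ECG finding, although that incidence is a named safety endpoint

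*SAP*

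**What the plan says.** Protocol 4.2.3 lists as its second safety endpoint "Incidence of abnormal findings in clinical safety laboratory parameters, vital signs, and ECGs". SAP Section 2 repeats it.

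The protocol describes the analysis in two places. The synopsis promises descriptive summaries of vital signs, ECGs and laboratory data by treatment arm and overall. Section 9.5.4.2 says "Vital signs and laboratory tests will be summarized as absolute values and change from baseline by treatment arm" and adds a tabulation of participants with fever (38°C or above) and of days with fever. The same section gives abnormal laboratory results and ECG data as listings only.

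The SAP plans the following:

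- Laboratory tests (6.3.2): "As collection date may vary, by-patient listings will be provided and abnormal results will be flagged". A second listing, of abnormal and clinically significant results, is conditional on there being data for it. Collection is required at screening, discharge, Day 28 and Day 40. In between, "Haematology and clinical chemistry are optional in reporting during the hospital setting".
- Vital signs (6.3.3): observed values and changes by study day and arm. Fever is not mentioned.
- ECGs (6.3.4): each tracing is recorded as normal, abnormal but not clinically significant, or abnormal and clinically significant. The output is "Listings of data collected will be provided by patient".

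SAP 1.1, which lists departures from the protocol's analyses, mentions none of this.

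**The concern.** An incidence is a count over a denominator. A named incidence endpoint needs at least one table giving that count by arm, with a rule for what counts as abnormal and who is in the denominator. Without it, the criteria and denominators would be chosen after unblinding, by whoever counts from the listings, or the endpoint would not be reported at all.

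The protocol also notes in 2.4 that this is the first study of the product in patients with pulmonary complications of COVID-19. A plain by-arm comparison of abnormal findings is what a reader of the safety section would look for.

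The move from by-arm laboratory summaries to listings is a change from the protocol. A reader relying on SAP 1.1 would not know that it had been made.

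**Working it through.** The documents give no figure to reproduce, so the check sets the endpoint's three components against the planned outputs.

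| Component | Protocol synopsis | Protocol 9.5.4.2 | SAP | n (%) abnormal by arm in SAP? |
|---|---|---|---|---|
| Laboratory tests | Summarised by arm | Values and changes by arm; abnormal results listed | Listing with flags (6.3.2) | No |
| Vital signs | Summarised by arm | Values and changes by arm; fever tabulated | Values and changes by arm (6.3.3) | No |
| ECGs | Summarised by arm | Listed | Listed (6.3.4) | No |

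1. **Endpoint against output.** None of the three components has a by-arm count in the SAP.

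2. **SAP against protocol.** Two protocol outputs are lost: the by-arm summary of laboratory values and changes, and the fever tabulation. The fever table was the only incidence of an abnormal finding that 9.5.4.2 planned. SAP 1.1 records other departures (the supplemental ITT analysis, two sensitivity analyses) but not these.

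3. **Protocol against itself.** The synopsis has ECGs summarised by arm; 9.5.4.2 has them listed.

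4. **The SAP's reason.** Varying collection dates are given as the ground for listing laboratory data. The same section requires collection at three fixed points after dosing (discharge, Day 28, Day 40), and SAP 5.4 summarises by nominal visit whatever the actual day. Vital signs, taken on every day in hospital, are summarised by arm. Varying dates may complicate the in-hospital data; they do not prevent tables at the required visits or an any-time count. The SAP gives no reason for listing ECGs.

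5. **Other routes to the data.** SAP 6.2.2.1 analyses eGFR, troponin, CRP, ferritin and D-dimer by arm, but as efficacy markers in the mITT population and as values and changes. SAP 6.3.1 tabulates treatment-emergent adverse events by arm. Protocol 7.1.9.1 lets an abnormal laboratory finding be an adverse event, but anticipated fluctuations of existing disease need not be reported, and 9.5.4.1 speaks of events not related to the disease. Adverse event incidence is in any case a separate safety endpoint in 4.2.3.

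6. **What a table could show.** SAP 6.2.4 gives 77 participants receiving study drug, without the split by arm. Assume 38 and 39. The rates below are also assumptions, for illustration.
   - Exact 95% interval for 4/39 (10.3%): 2.9% to 24.2%. For 0/39 the upper limit is 9.0%.
   - 95% half-width for a difference, 1.96 × √[p(1−p)(1/38 + 1/39)]:
     - p = 0.10: 1.96 × √(0.09 × 0.05196) = 13.4 percentage points
     - p = 0.20: 1.96 × √(0.16 × 0.05196) = 17.9 percentage points
     - p = 0.30: 1.96 × √(0.21 × 0.05196) = 20.5 percentage points

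**The case against.** The strongest reply has four parts.

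- **The SAP largely follows 9.5.4.2.** That section itself only lists abnormal laboratory results and ECGs. This is correct, and the SAP departs from it only on laboratory value and change summaries and on fever. But it shows that 9.5.4.2 did not serve the endpoint either, and it leaves the conflict with the synopsis.
- **The information is not lost.** Flagged listings are sorted by arm under SAP 5.1, so counts could be made by hand, and abnormalities reported as adverse events reach by-arm tables. Both are true. Neither is a pre-specified estimate, and the second passes through investigator judgement.
- **Changes may be explained later.** Protocol 9.4 allows them to be documented in the SAP or the study report, and SAP 1.1 defers some to the report. That permits disclosure but does not supply the table.
- **With 77 treated, the tables will be imprecise.** They will, as the intervals above show. That limits what they can conclude, not whether a named endpoint should be reported.

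A reader might also infer more than the documents support.

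- **Anti-drug antibodies.** "A listing of anti-drug antibody data will be provided" looks like part of the same gap, and protocol 2.4 treats immunogenicity as a critical safety concern. But antibodies are not in this endpoint, and no by-arm rate is promised for them.
- **In-hospital sampling.** The optional wording in SAP 6.3.2 seems to clash with "daily collection of vital signs, physical exam, concomitant medications and laboratory evaluations" in protocol 4.1. Both defer to routine care. The optional wording covers haematology and chemistry only, while the COVID-19 tests are scheduled every other day. Table 3 of the protocol, which sets laboratory timing, was not legible in the copy read.
- **Enrolment hold rule.** It might seem that the rule on Grade 3 or higher laboratory abnormalities (protocol 5.5) is weakened by optional reporting, or by the rule that "the results from the first set of daily labs collected will be reviewed for this study and entered in the CRF". The hold rule turns on the investigator's assessment of significance and relatedness, not on entry of a value in the CRF.

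**Conclusion.** The point holds in this form: a safety endpoint named in both documents has no planned by-arm estimate in the SAP for any of its three components, and the loss of the protocol's by-arm laboratory summary and fever tabulation is not recorded in SAP 1.1. The protocol's synopsis and 9.5.4.2 also disagree on ECGs.

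It would go too far to say that the trial can reveal nothing about abnormal findings by arm. Listings, adverse event tables and the marker analyses give partial views.

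The size is a reporting gap in one safety endpoint, with no effect on the primary analysis. It should be closed before final database lock, and SAP Section 1 leaves room for an amendment until then. The conclusion rests on the text of the two documents alone; only the precision figures depend on the assumed 38/39 split and the illustrative rates.

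**What to change.** In SAP 6.3.2 to 6.3.4, add Safety Population tables by arm:

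- Laboratory: n (%) with any post-baseline abnormal result and any clinically significant result, per parameter; values and changes from baseline at discharge, Day 28 and Day 40.
- ECG: n (%) with an abnormal tracing and with an abnormal, clinically significant tracing, using the categories already recorded. Show the number with an ECG at each visit, since it may be omitted at remote visits.
- Vital signs: n (%) with an abnormal value, and the protocol's fever table. SAP 6.3.3 reports temperature in Fahrenheit, so state the threshold in both units (38 × 1.8 + 32 = 100.4°F).

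State the abnormality criteria before unblinding, and take participants with a post-baseline value as the denominator. Because in-hospital sampling is uneven, show fixed-visit results beside any-time results. Reconcile the synopsis with 9.5.4.2 on ECGs.

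If the tables are not wanted, record the departure in SAP 1.1 with the reason.

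A one-line count by arm of treatment-emergent anti-drug antibodies would be a sensible optional addition, though it is not part of this endpoint.

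The cost is a few standard tables and the work of fixing criteria. No new data collection is needed. The downside is several imprecise estimates, which should be presented descriptively with intervals.
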